For those women who are breast-feeding during the postpartum PK visit and wishing to participate in the breast feeding component, and if the CRC allows infants to come to the unit with their mothers, we will obtain breast milk at baseline prior to the morning BUP dose and approximately every 2-4 hours post dosing using an automated breast pump to empty the breasts. We will use at least 1 mL but not more than 5 ml of the milk for analysis of drug and metabolite concentrations and allow the mother to use the remaining milk for her infant. If these women participated in the post delivery ancillary study of breast milk, they can still participate in the postpartum PK breast milk study.

For those women consenting to the postpartum PK study, we will obtain infant blood by heel stick once prior to a feeding and again 1 hour after the feeding. Optimally this will be done during the feeding that is as close to the BUP dose as possible. In total, no baby will have more than 8 heel sticks, 6 while in the hospital or during a postpartum PRC visit as part of the postpartum ancillary study and 2 in the postpartum PK study. If the subject is not participating in the BUP PK study, the baby will have up to a maximum of 6 heel sticks (trough and peak levels on 3 occasions) as part of the postpartum ancillary study.

Upon completion of all biological fluids collection, the venous catheter will be removed and the subject will be discharged to home.

D.5.vii. Physiological Testing (Applicable to Subjects in the PK Study):

Pupillary diameter will be determined using a hand held pupillometer device (PLR-200™ Pupillometer- Neuroptics Irvine Cal.), galvanic skin response will be obtained using the Mind Ware Mobile Impedance Device, heart rate and blood pressure will be recorded by standard means. The Cravings and COW scores will be performed in conjunction with physiologic assessments at the following times:

Sample/Measurement Type	Dosing	Time Interval
physiologic	BID	Baseline and 30, 60, 90, 120, 240, 360, 480, 600, 720 minutes post dose
physiologic	TID	Baseline and 30, 60, 90, 120, 240, 300, 360, 420, 480 minutes post dose
physiologic	QID	Baseline and 30, 60, 90, 120, 240, 300, 360 minutes post dose
physiologic	5 times/day	Baseline and 30, 60, 90, 120, 180, 240, 300, minutes post dose

D.5.viii. Dietary Restrictions (Applicable to Subjects in the PK Study):

Subjects will be required to fast (other than water) after midnight prior to the study visit, and for two hours after the study drug is administered. Participants may not consume grapefruit juice within 3 days prior to the study visit. Two to three hours after the subject takes her morning BUP dose, subjects may receive a meal, and then will continue to receive meals in the CTRC or MWH for the duration of the study visit with snacks as requested. Subjects will be encouraged to consume at least 100 mL of water per hour in order to maintain adequate urine flow.

D.5.ix. Delivery Specimens (Applicable to all Subjects):

A urine sample will be collected for a comprehensive drug screen within 48 hours of admission for delivery. Samples from subjects with a positive drug screen at delivery will not be used for specific aim 5 of the study.

Prior to delivery, maternal blood specimens (for BUP and PBMC analysis) will be collected, when possible.

At the time of delivery, a cord blood specimen, a placenta sample (3x3 cm), and an umbilical cord sample (3 inches) will be collected, when possible. The umbilical cord and placenta samples are immediately frozen at -80 degrees. Refer to section D.5.xi below for maternal and cord blood sample collection and processing instructions.

Additionally, a sample of maternal hair will be collected by research staff from an inconspicuous part of the scalp, as close to delivery as possible, but not to exceed 3 days post-delivery.

Labor and Delivery biological specimens (including the urine drug screen) will be collected when possible.

D.5.x. Neonatal Evaluation and Care (Applicable to all Subjects):

All infants of subjects in this trial will be evaluated for Neonate Abstinence Syndrome according to study criteria. Treatment of withdrawal will be standardized to the degree possible. At Magee the assessment for symptoms of withdrawal is performed every 2-4 hours with the Finnegan Scoring system. Morphine is initiated as the drug of choice for infants with opioid exposure when the averages of three consecutive scores are ≥ 8 , according to the scoring system and treatment plan at Magee.

When possible, a sample of newborn scalp hair will be obtained, as close to delivery as possible, but not to exceed 3 days post-delivery.

D.5.xi. Blood and Saliva Collection and Processing:

The following collection and processing instructions apply to all blood and saliva samples collected during this study. The samples collected will be dependent on which parts of the study the subject participates in.

Blood samples will be collected as follows:

- Maternal and Cord Blood Samples for BUP Analysis: One 10 mL heparinized vacutainer tube will be drawn at the time points described in sections D.5.vi and D.5.ix. The tube should be centrifuged at 1500 g at 4°C for 15 minutes. Plasma samples will then be transferred into polypropylene tubes and frozen at -80 degrees centigrade until analysis.
- PBMC analysis: One 5 mL EDTA vacutainer tube will be drawn with the first sample (pre-dose) at each PK study visit and at delivery (applicable to all subjects), when possible. The sample should be stored at room temperature. Notify [name] lab in advance at [contact] / [contact] or via email ([contact]) to allow for pick up and processing within 4 hours of collection.
- DNA Analysis: One 10 mL EDTA vacutainer tube will be drawn at the Baseline Screening Visit. If the DNA sample is unable to be obtained at the screening visit, it may be collected anytime during the study when blood is being drawn. The sample should be frozen at -80 degrees centigrade until analysis.

Saliva samples will be collected using a Sarstedt Salivette collection device. The salivary collection sponge can be centrifuged later in the day. Salivary pH will be determined. Oral fluid samples will then be transferred into polypropylene tubes and frozen at -80 degrees centigrade until analysis.

D.5.xii. Study Outcome Measures and Ascertainment (Applicable to all Subjects):

Mothers and infants will be followed until they are discharged from the hospital, at which time relevant data from the labor, delivery and nursery records will be recorded.

a. Primary Outcome:

The primary outcome is the exposure to BUP (AUC) during pregnancy and the post-partum state.

b. Secondary Outcomes Maternal:

Other maternal outcomes to be measured are:

1. The relationship between COW and Craving scores, pupillometry, heart rate, blood pressure

and GSR scores to the maternal plasma concentration of BUP and its major metabolites

2. The impact of polymorphisms of CYP 450 and conjugating enzymes of buprenorphine on plasma concentration of BUP and its major metabolites
3. The relationship between the umbilical cord and maternal concentration of BUP and its major metabolites
4. The relationship between maternal dose and concentration of buprenorphine and metabolites in umbilical cord, maternal and infant hair
5. The relationship between maternal plasma and breast milk concentrations of BUP and major metabolites
6. Cumulative amount of BUP and its metabolites excreted in breast milk.

c. Secondary Outcomes Neonatal:

Neonatal outcomes to be measured include the following:

1. Relationship between concentrations of BUP and its metabolites in maternal and umbilical cord plasma and maternal and newborn hair and maternal dose and parameters of neonatal withdrawal
2. Infant hospital days
3. Birthweight
4. Gestational age
5. Neonatal Complications including: Respiratory distress syndrome (RDS), stillbirth, neonatal death, intraventricular hemorrhage as determined by cranial ultrasound, bronchopulmonary dysplasia, necrotizing enterocolitis, early onset of neonatal sepsis, seizures, retinopathy of prematurity (ROP), and hyperbilirubinemia.

D.5.xiii. Statistical Considerations

Data Analysis Plan:

The primary outcomes will be the area under the plasma concentration x time curve (AUC) of BUP during early pregnancy compared to the AUC in late pregnancy. We will also compare the AUC of BUP and metabolites during early and late pregnancy and the post-partum period. Mixed-effect models, repeated measures ANOVA or paired t-testing, will be used to compare early to late-pregnancy and overall pregnancy values to the postpartum values. Secondary outcomes such as metabolite concentrations will be analyzed in the same fashion. Additional analysis will also include multiple regressions to evaluate the relationships between maternal and fetal plasma concentrations of BUP and its metabolites, placental p-glycoprotein, physiologic parameters and CYP3A4/5 expression. We will also use population pharmacokinetic analysis to evaluate the contribution of various covariates (i.e. maternal genotype, BMI, etc.) to the observed variability in the trough plasma concentrations of BUP.

Primary Hypothesis

Based on data from our recently completed study, the dose-adjusted AUC was 2.34 ± 1.82 (ng/ml).hr in pregnant women at a mean gestational age of 34 weeks. In postpartum women, the dose adjusted AUC was nearly 100% higher at 4.0 ± 2.8 (ng/ml).hr. We anticipate that the AUC in the first half of pregnancy will be somewhere between values of non-pregnant women and those of pregnant women in the latter part of pregnancy. The sample size required to demonstrate a 50% difference between the dose adjusted AUC in the first half of pregnancy and the second half of pregnancy as well as a 50% difference between the dose adjusted AUC in the first half of pregnancy and the postpartum state is 37 ($\alpha = 0.05$, $\beta = 0.80$). We will recruit an additional 3 subjects to

account for dropouts or noncompliance. The secondary physiological outcomes will also be addressable with this sample size as the variance in pupil measurements is small (4.65 ± 0.4 mm at baseline and 2.64 ± 0.08 mm at 2 hours in the paper of Middleton et al¹³) and each patient will provide data from 2-3 PK studies. Thus there will be 120 studies that relate a physiologic variable to plasma buprenorphine. Specific Aim 5 which relates NAS to various parameters (maternal dose, maternal and cord plasma buprenorphine /metabolite concentrations etc.) can be addressed with the projected sample size as correlations between the dependent variable NAS and the numerous independent variables i.e. maternal dose, maternal concentration at delivery, maternal hair concentration, cord blood concentration, newborn hair concentration etc. can be performed with samples size of 15. We assume that 50 % of these infants will have some degree of NAS so the sample size of 40 should be sufficient. If the prevalence of NAS is lower, we can recruit additional subjects. Since the extensive PK studies will not be required to test this hypothesis, recruitment should be easier and can be done at secondary sites if needed.

Secondary Hypotheses

Patients will be at steady state when the pharmacokinetic studies are performed. This will be documented by comparing the concentration at time 0 and at 12 hrs. (less than 20% variation). Plasma concentration-time profiles will be analyzed using both non-compartmental and population pharmacokinetic modeling and simulation approaches. Data will be analyzed using WINNONLIN and NONMEM software. We will compare various pharmacokinetic parameters between pregnant and non-pregnant (postpartum) subjects using a paired t-test as described previously. This will include all non-compartmental data (C_{max}, T_{max}, AUC(0-t), AUC(0-∞), k_e, λ_Z, CL/F, CLR, V_d/F, V_{ss}, AUMC, and MRT). Population pharmacokinetic model will be developed using nonlinear mixed effects modeling software (NONMEM version 7.1; ICON Development Solutions, [name]), GNU Fortran 95 compiler and PLT tools (version 5.1.0). The general linear model under steady state will be constructed using ADVAN5 SS5 subroutines. In order to identify the covariates that influence the pharmacokinetics of BUP, the following covariates will be evaluated: maternal age (years), body weight (kg), race, gestational age, serum albumin, serum creatinine (mg/dL), salivary PH, buprenorphine dose, tablet size and co-medications and SNPs of the various metabolizing enzymes. For covariate selection, univariate analysis with stepwise forward addition ($p < 0.01$) and backward elimination ($p < 0.001$) procedures will be followed. The covariates that significantly influence the pharmacokinetics of BUP and its metabolite will be incorporated in the final model. The predictive performance of the model will be internally evaluated using prediction corrected-visual predictive check, where 1500 data sets will be simulated using the parameter estimates in the final model. The 50th percentile concentration (median) and the 5th and 95th percentile concentrations (90% prediction interval) will be plotted and compared to the observed concentrations. The data obtained will be used to validate the predictions of SIMCYP-PBPK simulation from the basic/translation project.

D.6. Preliminary Data Relevant to the Primary Outcome

We have developed a HPLC-MS-MS assay for BUP and metabolites with a lower limit of quantitation of the assay for BUP (BUP), of 0.05 ng/ml, while that for nor-BUP is 0.5 ng/ml. We have performed an intensive PK study on 12 subjects. The dose-adjusted AUC in the third trimester of pregnancy (2.4 ng/ml).hr was lower than in the postpartum period (4.0 ng/ml).hr while clearance is higher in pregnancy (589 L/hr) than in the postpartum period (288 L/hr). There was a large variation (cv = 50%) in both AUC and clearance values. None of the subjects in this cohort was studied in the first half of pregnancy.

D.7. Potential Problems, Alternative Strategies, Benchmarks

Recruitment is a potential problem in any clinical trial and if other sites in the OPPTB do not have access to patients on BUP in their own institutions they may have difficulty recruiting subjects. These patients have difficulty with compliance to drug treatment regimens so dropout may be higher than in most clinical trials. Postpartum studies are difficult because of childcare issues and this may hamper recruitment. These challenges can be overcome by identifying physicians and clinics that write prescriptions for BUP and care for such patients. The childcare issue can be addressed by financial incentives or by allowing the mother to bring her baby to the CRC during study days.

D.8. Feasibility

The sample size for this study is not large and the number of patients on BUP is increasing. We started a BUP clinic in July 2014 and as of mid-November we have 30 patients in the system. We estimate acceptance rates of 33% given time requirements. The other OPRC sites appear to have limited BUP patients delivering at their institutions which impact their ability to carry out all aspects of this study. Potential subjects however can be recruited at clinics that provide opioid substitution maintenance therapy to pregnant women. The CRC studies do not require the patient to deliver at the OPRC hospital. Likewise cord blood and maternal blood at delivery can be obtained for other institutions where these patients deliver. Follow-up of the infants in non-OPRC hospitals will be a challenge and therefore Hypothesis 5 may require that more infants be studied at Pittsburgh than the other sites. Given our increasing volume of BUP patients we should be able to recruit additional subjects at the Pittsburgh site if necessary. This study contributes to the primary aims of the OPRC as the issue of opioid substitution therapy is clinical very relevant and the lack of PK/PD information to provide clinical guidance begs for such studies to be done.

D.9. Sample Analysis and Collection of Negative Control Samples

Biological specimens will be collected and labeled with the study and subject number only and stored in locked freezers at MWH or the Magee Women Research Institute. Only the study research staff will have access to individually identifiable private information. Biological specimens will intermittently be sent to [name] lab at the University of Pittsburgh for analysis. Samples sent for analysis will not contain any identifiable information. Patient demographics necessary for pharmacokinetic analysis will also be blinded and sent to [name] lab.

Negative Control Samples: Biological samples from women who are not taking BUP are required as negative controls. Subjects potentially eligible as negative controls will be identified by reviewing the medical records of patients presenting for prenatal or postpartum care at private offices or the MFM offices at MWH. Patients will be approached by their care provider or a co-investigator about the study. Healthy volunteers serving as negative controls will be recruited prior to delivery or within 12 months after delivery. Subjects recruited as negative controls will be asked to sign a separate consent allowing for the collection of samples.

The negative control samples will be collected during pregnancy, delivery or postpartum, as requested by [name] lab, and according to study procedures. The biological samples may include any of the following: urine, saliva, placenta, umbilical cord blood, umbilical cord tissue, maternal hair, infant hair, and breast milk.

D.9.i. Eligibility Criteria for Volunteers Serving as Negative Controls

Inclusion Criteria:

1. Age between 18 – 45 years
2. Current pregnancy or delivery within the last 12 months
3. Able to give informed consent and undergo study procedures

Exclusion Criteria:

1. Currently taking buprenorphine

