Substance abuse costs our nation over \$600 billion annually. Drug addiction treatment reduces drug use and has been shown to reduce the health and societal cost far more than the actual cost of the treatment. Treatment is also much less expensive than other options. Outcomes of drug treatment programs are dependent on adequate treatment length and drop out is one of the major problems in the current treatment program. It is therefore critical to optimize drug dosing regimens in patients to improve adherence and success of the treatment programs. In 2012, an estimated 400,000 adults aged 18 or older were current illicit drug users. Many of these were pregnant women. In the most recent National Survey on Drug Use and Health (2012), 6% of pregnant women reported using illicit substances within the past 30 days¹. Azadi et al found that 3% of women were urine-positive for illicit opioids at the time of delivery². Currently, the standard of care for an opioid-dependent pregnant woman in most institutions is methadone, however buprenorphine (BUP) is also used for this indication as it is FDA-approved for opioid addiction although not specifically for pregnant women. There has been increasing evidence that BUP may have comparable efficacy to methadone, and may have fewer severe neonatal complications especially neonatal abstinence syndrome (NAS). In a recent study, BUP-exposed, as opposed to methadone exposed, neonates required significantly less morphine for treatment of NAS, had significantly shorter duration of treatment for NAS and had significantly shorter hospital stays³. Methadone, a full μ agonist, has significant adverse reactions such as Q-T prolongation, potential for life-threatening respiratory depression and extreme sedation⁴⁻⁶. Conversion from illicit narcotic use to methadone commonly requires hospitalization for 3-4 days as the dose of methadone is titrated upward based on the patient's symptomatology^{4,5}. Upon hospital discharge methadone treated patients receive daily dosing of medication at outpatient clinics that monitor the patients for continued illicit drug use. This requirement is extremely burdensome on the patients since many do not have transportation and they must arrive at the clinics in the morning. BUP, a partial μ agonist, has decreased severity of adverse reactions and therefore physicians are able to convert patients on an outpatient basis. The patient is given a 1-4 week supply of oral medication thus eliminating the burdensome task of attending daily clinics for drug administration. These benefits of BUP are changing the management of drug addiction dramatically and more institutions will turn from in-patient treatment with methadone to the outpatient strategy with BUP. The American College of Obstetricians and Gynecologists in its 2012 Committee Opinion indicates that the literature "supports the use of buprenorphine as first line treatment for pregnant opioid –dependent women"⁷. Similarly the American Society of Addiction Medicine supports the use of buprenorphine in opioid- addicted pregnant women⁸ and the World Health Organization (WHO) which encourages availability of a buprenorphine option has described the worldwide availability of buprenorphine⁹. The dosing of BUP currently is based on studies in men and non-pregnant women and limited animal data that related plasma concentrations of BUP to the degree of saturation of the μ receptor in the brain¹⁰⁻¹³. These studies suggest that a dose of 16 mg daily saturates 95% of the μ receptors. The plasma half-life in non-pregnant subjects is approximately 22 hours and therefore a dose of 16 mg/day appears to be sufficient to saturate the receptors. The standard recommended dosing regimen for sublingual BUP is therefore 8 mg bid or 16 mg QD. Unlike for methadone, where increased dosing is recommended during pregnancy, currently there are no guidelines on dosing BUP in pregnant women. The dosing regimen used in non-pregnant subjects does not appear to be adequate for pregnant women. Dosing is adjusted to the patient's symptomatology using the Clinical Opiate Withdrawal (COW) score, some of which is subjective and some based on objective physiological parameters. The failure rate for BUP is highest (33%) during the induction period i.e. the time from stopping illicit drug use to the point of achieving a stable dose of BUP³. This suggests that the current treatment regimens for BUP are inadequate for many women. Indeed at Magee-Womens Hospital, using COW scores to determine a dosing regimen has resulted in many women requiring doses higher than the 16 mg daily dose used in non-pregnant subjects. The high failure rate of BUP during induction and the experience at Magee are

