
B. Innovation

Our proposed project challenges the current clinical practice paradigm that defines a dose of BUP for pregnant women that is based on pharmacokinetics in men and non- pregnant women and relies on the COW score to titrate the dose. We will define the pharmacokinetics and pharmacodynamics of BUP in early and late pregnancy and the postpartum period and determine what contributes to the variation in plasma concentrations and response. We will also relate plasma concentrations of BUP and its major metabolites to physiologic parameters that can be used to gauge the amount of drug in mother’s plasma. Our expectation is that we will demonstrate that higher doses of BUP are needed throughout pregnancy and that the dosing regimen can be adjusted using patient covariates and biophysical measurements in addition to the COW scores. Our exploration of pupillometry and the galvanic skin response to gauge maternal BUP satiety in pregnancy is unique and challenges contemporary practice¹⁵⁻¹⁷. There is a strong relationship between plasma BUP concentrations and the saturation of brain μ receptors¹². If μ receptor occupancy is a major determinant of maternal satiety and drug-seeking behavior, then plasma concentrations of BUP and its metabolites are key in achieving these outcomes. Any variation in dosage requirements cannot be attributed to differences in blood brain barrier permeability but may rather reflect differences in absorption or metabolism or elimination of BUP or its metabolites. Therefore, to optimize therapy a direct or indirect measure of plasma BUP is needed.

Measurement of BUP concentrations in plasma requires high sensitivity equipment and therefore not likely to be useful in clinical practice. An indirect non-invasive measure of BUP plasma concentrations is appealing due to convenience, low cost and rapidly available results. COW scores are now the standard by which buprenorphine is dosed but they are flawed as half the parameters are subjective and can be manipulated by the patient. A purely physiological endpoint is less likely to be controlled by the patient. We will evaluate several maternal and newborn variables that might be predictive of NAS. Our approach is unique in that we will have full pharmacokinetic characterization of the mother as well as hair samples and placental P-gp status to enable a much more complete assessment of predictive factors in combination that have previously been reported singly.

C. Specific Aims

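### For Aim 3 the plan names only multiple regression of markers and plasma BUP, with no concentration-effect form or repeated-readings structure; under its own saturation premise, a linear fit could misstate a pregnancy difference in either direction.

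*Combined protocol and SAP*

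**What the plan says.** Section B (Innovation) sets the goal: "We will also relate plasma concentrations of BUP and its major metabolites to physiologic parameters that can be used to gauge the amount of drug". Aim 3 in section C evaluates pharmacodynamic endpoints in pregnancy and in the non-pregnant state. Maternal secondary outcome 1 (D.5.xii) is the relation of COW and craving scores, pupillometry, heart rate, blood pressure and GSR to plasma BUP and metabolites.

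The method is in D.5.xiii, Data Analysis Plan: "multiple regressions to evaluate the relationships between maternal and fetal plasma concentrations of BUP and its metabolites, placental p-glycoprotein, physiologic parameters and CYP3A4/5 expression". No linear, logarithmic or saturable form is given. Nor are woman or visit effects, although D.5.vii schedules 8 to 10 readings per visit and D.1 plans up to three visits per woman. The nonlinear mixed-effects work under Secondary Hypotheses concerns pharmacokinetics only.

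The pharmacology in the same document is saturable. Section A: "These studies suggest that a dose of 16 mg daily saturates 95% of the" μ receptors. Section B: "There is a strong relationship between plasma BUP concentrations and the saturation of brain" μ receptors. Section B also supposes, introduced by an if, that "receptor occupancy is a major determinant of maternal satiety and drug-seeking behavior".

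**The concern.** On a saturable curve, the slope of a straight line depends on which part of the curve the data cover. If concentrations differ between pregnancy and postpartum, a linear fit can show a difference in marker response when the underlying curve is the same. The protocol hopes to use such markers alongside COW scores to adjust dosing, so an artefact of the concentration range could be read as a finding about pregnancy.

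A second problem does not depend on comparing states. On a plateau the marker barely moves while concentration changes severalfold. A regression without a saturable form would not show where a marker stops being informative. Regression without woman and visit effects would also treat correlated readings as independent.

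**Working it through.** **The plan's own figures.** No sample size or precision figure is given for this analysis. D.5.xiii offers 120 studies relating a physiologic variable to plasma BUP. That is 40 × 3, so it needs every woman to complete all three visits, although D.4 requires only one. It says nothing about the shape of the curve.

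**Inputs**
- Saturation: 95% at 16 mg daily (section A, from men, non-pregnant women and limited animal data).
- Exposure (D.5.xiii): "the dose-adjusted AUC was 2.34 ± 1.82 (ng/ml).hr in pregnant women", and postpartum "the dose adjusted AUC was nearly 100% higher at 4.0 ± 2.8 (ng/ml).hr". The ratio is 4.0/2.34 = 1.71, so 71% higher rather than nearly 100%.
- Clearance (D.6): 589 and 288 L/hr, ratio 2.05.
- Pupil diameter (D.5.xiii): 4.65 ± 0.4 mm at baseline and 2.64 ± 0.08 mm at 2 hours.
- Assumed: the marker is proportional to hyperbolic occupancy, E = C/(EC50 + C); a postpartum woman on 16 mg daily is at 95%; the pregnancy/postpartum dose ratio, which the documents do not give, lies between 1.0 and 2.5.

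**Slope ratio for one unchanged curve**
- 95% occupancy gives C/EC50 = 0.95/0.05 = 19 postpartum.
- In pregnancy, C/EC50 = 19 × dose ratio/1.71. At equal dose this is 11.1, and occupancy is 11.1/12.1 = 91.7%.
- The local slope is proportional to 1/(1 + C/EC50)². At equal dose the pregnancy/postpartum ratio is (20/12.1)² = 2.7.

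| Pregnancy/postpartum dose | C/EC50 in pregnancy | Slope ratio, linear in C | Slope ratio, linear in log C |
|---|---|---|---|
| 1.00 | 11.1 | 2.7 | 1.6 |
| 1.25 | 13.9 | 1.8 | 1.3 |
| 1.50 | 16.7 | 1.3 | 1.1 |
| 1.71 | 19.0 | 1.0 | 1.0 |
| 2.00 | 22.2 | 0.74 | 0.87 |
| 2.50 | 27.8 | 0.48 | 0.71 |

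The log column uses C/(1 + C/EC50)². A log transform shrinks the artefact but does not remove it.

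**Sensitivity**
- Assuming 80% to 98% saturation instead of 95% moves the equal-dose ratio only from 2.2 to 2.8.
- With the clearance ratio 2.05, the equal-dose value is 3.8, and the ratio reaches 1 at a dose ratio of 2.05.
- Simulated straight-line fits at equal dose gave 2.3 to about 3 across different assumed set-ups, mostly 2.6 to 2.9. At a dose ratio of 1.71 they gave about 1.

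**False state differences.** Pupil noise as a share of the baseline-to-2-hour change (4.65 − 2.64 = 2.01 mm) is 0.08/2.01 = 4% or 0.4/2.01 = 20%, depending on which ± value is used. The documents do not say whether these are standard deviations. At equal dose with one common curve, a concentration-by-state interaction on the linear scale reached p < 0.05 in 78% to about 100% of simulated trials at 2–4% noise, and in about half (49–52%) at 20% noise. At a dose ratio of 1.5 and 20% noise the rate was about 10%. Testing state on EC50 with a common Emax kept false positives at about 3–10% in every setting tried, although EC50 itself was poorly estimated at 10–20% noise.

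**Gauging.** From 0.5 to 2 times the 16 mg concentration, occupancy runs from 9.5/10.5 = 90.5% to 38/39 = 97.4%. A reading of 95% ± 4 points corresponds to (0.91/0.09)/19 = 0.53 up to (0.99/0.01)/19 = 5.2 times that concentration. With ± 20 points there is no upper bound.

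**The case against.** A reader might infer that markers will look more responsive in pregnancy. The documents do not support that. The values 2.34 and 4.0 are dose-adjusted, whereas a marker responds to actual concentration. Doses are titrated to symptoms, many women need more than 16 mg daily (section A), higher doses in pregnancy are expected (section B), and clinical management is not mandated (D.5.iii). The direction is therefore unknown. Equal dose is one scenario; section A itself mentions women kept on pregnancy doses after delivery.

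A reader might also infer that the plan commits to a straight line. It does not: multiple regression can carry transformed or curved terms. The gap is an unspecified form.

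Nor does the plan write a concentration-by-state test. D.3 asks in words whether smoking modifies the marker-concentration relation, but asks no such question for pregnancy. The error rates above therefore belong to an analysis that Aim 3 invites, not to one that is planned.

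Three further objections carry weight. The occupancy link is conditional and concerns satiety, not pupil or skin response. An Emax fit may be imprecise on noisy plateau data. The work is secondary and exploratory, and D.3 concedes that sample size may be inadequate for some questions.

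It could also be said that D.5.xiii already names mixed-effect models and extends the approach to secondary outcomes. That sentence concerns comparing values between periods. Physiologic parameters appear in the next sentence, with multiple regression only.

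These objections remove any claim of a known direction or a fixed error rate. They leave the missing model, and uncontrolled dosing strengthens the case for stating one: neither the size nor the sign of a spurious difference could be known in advance.

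**Conclusion.** The point holds as a gap in specification. For maternal secondary outcome 1 the plan gives no concentration-effect form and no structure for repeated readings, while its own premise puts typical concentrations near a plateau.

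If markers follow hyperbolic occupancy, a fit linear in concentration may show a spurious pregnancy difference of either sign. The slope ratio is about 2.7 to 2.9 at equal dose, about 1 at a dose ratio of about 1.7 (2.05 on the clearance figures), and below 1 beyond that. How often it would be declared significant depends on marker noise, which the documents do not fix. The gauging problem rests on the same occupancy assumption but not on any dose difference between states.

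The change is worth making because it is cheap. It does not touch the primary AUC comparison.

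**What to change.** In D.5.xiii, for physiologic markers against plasma BUP:
- Specify a mixed-effects concentration-effect model with woman and visit effects.
- Make the primary form saturable (Emax), with a linear or log-linear form as the stated fallback if Emax is not identifiable.
- Assess any pregnancy-state difference on EC50 with a common Emax, adding state on Emax only if it can be estimated. Do not assess it on a linear slope.
- Limit any claim that a marker gauges plasma BUP to the concentration range in which the fitted curve can resolve a stated change, for example two-fold.

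The cost is analysis-plan wording and modest extra modelling in NONMEM, which is already planned; no new data are needed. The downside is one or two more parameters, and EC50 may be imprecise if most readings lie on the plateau. That imprecision should be reported, since it shows how little the marker says about concentration there.
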